Screening/Eligibility: During screening, eligibility will be determined using scripted questions: Inclusion/Exclusion Criteria. Potential subjects will be invited to participate in the study, demographics will be recorded. **Inclusion Criteria:** Postmenopausal women with clinically diagnosed vulvovaginal atrophy, age ≥ 55 years old and a screening vaginal pH of ≥ 5 , without menses for ≥ 12 months, no uterovaginal or vaginal vault prolapse beyond the hymen. **Exclusionary Criteria:** 1) Patients with BMI $\geq 35\text{kg}/\text{m}^2$. 2) Any patients with infections requiring antibiotic or antifungal therapy during the study period or within the last month or during the study period. 3) Study patients may not use any vaginal suppositories, douches, or vaginal hygiene wipes within the month preceding enrollment. 4) Patients receiving ongoing hormone replacement therapy. Patients already on hormone therapy, will be allowed to undergo a "wash out" period of estrogen or progesterone products for one month prior to enrollment. 5) Patients requiring concurrent use of steroid creams for other indications (e.g. lichen sclerosis). 6) Additional exclusions included patients with systemic conditions requiring immunosuppressive drugs, currently receiving chemotherapy, or history of pelvic radiation. 7) Any patients with contraindications to vaginal estrogen therapy including vaginal bleeding of unknown etiology. 8) Any patients with history of connective tissue disease. 9) Current tobacco use.

D.2. Study Design

The intention of this study is for each of the subjects to serve as her own control. Twenty patients will receive the treatment intervention. Five will not receive the treatment intervention. The five subjects not receiving

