treatment are intended to serve as a control cohort to demonstrate stability of the microbiome over the study period. It is anticipated that unlike premenopausal subjects, the postmenopausal subjects not undergoing treatment (control group) will have little variation of the microbiome over the eight weeks. Each of the twenty-five subjects will be sampled for microbiome and inflammatory biomarker analysis at three different locations (vagina, bladder, rectum) at two separate time points (Baseline Visit 1 and after eight weeks of vaginal estrogen therapy, Visit 2). This will yield a total of 300 samples for the study. The treated subjects (20) and untreated (5) subjects may be compared to each other but that is not the primary aim of this study.

Intervention: 1g conjugated estrogen (CE) cream given nightly for 2 weeks then twice-weekly to complete planned eight weeks therapy. This specific dose and frequency has been shown to improve objective and subjective measures of vaginal epithelium in previous studies (23, 27). It has also been shown to achieve objective improvements in as little as three to four weeks (23). Additionally, this dose and regimen is already commonly used and will provide excellent external generalizability.

D.3. Specific Aims

D.3.1. Specific Aim – 1: To assess the quantitative change in relative abundance of Lactobacillus among the community composition of bacteria in the vagina pre- and post- vaginal estrogen therapy. **Hypothesis:** A statistically significant quantitative increase in the relative abundance of Lactobacillus will be seen.

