Based on these results, we expect the relative abundance of Lactobacillus in our cohort to be somewhere between 0.112-0.532 at baseline. As the selection criteria of our cohort does not include VVA symptomatology, we expect the relative abundance of Lactobacillus spp to be approximately 0.4 ± 0.3 . **With a Type-1 error of 0.05, we estimate with 80% power that we can detect an effect size of 0.2 increase (0.4→0.6) in the relative abundance of Lactobacillus spp with a treatment sample size of 20 patients.**

Biostatistical Analysis Plan: The following microbial community-level analyses will be performed to investigate the overall microbiome differences between the pre-treatment and post-treatments groups using the R package **phyloseq** (Table 2)(32).

Table 2. Overview of Community-Level Microbiome Analysis

Outcome	Measurements	Two-group comparisons
Alpha diversity (diversity within a sample)	Shannon, Chao, Simpson indices	t-tests, Mann-Whitney U
Beta diversity (diversity between samples, overall microbiota composition)	Bray-Curtis, unweighted UniFrac, weighted UniFrac (represented by PCoA to visualize clustering)	PERMANOVA or Dirichlet-multinomial distribution with Wald-type test

To identify individual taxa significantly associated with vaginal estrogen treatment, taxa-specific analyses will be performed. Given the distinct properties of microbiome data (compositional counts/proportions, varying total sequence reads across samples, over-dispersion), microbiome counts, transformations of microbiome counts, and beta regression for relative abundance will be used (33-39). To deal with zero-inflation of microbiome data, we will employ zero-inflated models: negative binomial (for count data), Gaussian (for logarithm or arcsine square root transformations), beta regression (for relative abundance) – which allow analysis of multiple covariates which may vary between treatment and non-treatment groups (38, 40-43). An R package *bmzim* for these models will be used. Standard procedures (e.g. Holm's, Hochberg's, Hommel's, Benjamini and Hochberg's methods) will be used to calculate p-values adjusted for multiple comparisons.

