D.3.2. Specific Aim – 2: To evaluate the VMI, vaginal pH, and vaginal inflammatory biomarkers: IL-1B, IL-4, IL-6, IL-8, IL-10, TNF- α , MCP-1, GM-CSF and correlate any notable changes with changes noted in the vaginal microbiome. **Hypothesis:** An overall measured decrease in the levels of vaginal inflammatory biomarkers in response to therapy as well as an increase of the VMI with concomitant lowering of the vaginal pH, all signifying a return of the vaginal environment to a healthier state will occur. These changes will be highly correlated with increased Lactobacillus predominance.

Approach: The VMI, vaginal pH, and vaginal inflammatory biomarkers: IL-1B, IL-4, IL-6, IL-8, IL-10, TNF- α , MCP-1, GM-CSF will be collected at the same time points (V1 and V2). Changes in these data points will be correlated with changes noted in the vaginal microbiome (see below). As was used in a previous study (27), the VMI served as a tool for measure of adherence to vaginal estrogen application but also as an objective standard by which to correlate changes in the vaginal microbiome.

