Biostatistical Analysis Plan: Mean inflammatory marker concentrations and VMI scores will be compared by Student t-test or robust non-parametric tests between pre- and post-treatment samples. Normal linear regression will also be used to test the difference of the two cohorts (cytokine concentrations as response, cohort indicator as covariate). Similar methods will be used to analyze the difference in cytokine levels from V1 and V2 between groups. We will use three methods to investigate the relationship between bacterial taxa and cytokine levels: 1) Pearson's correlation coefficients will be calculated between cytokine levels and bacteria taxa (measured by percentage of reads) with a heat map showing correlations that are significantly different between pre- and post-treatment groups. To determine if cytokine levels and microbiota contribute to the clustering of women pre- and post-treatment, PCoA will be used to determine if these groups separate in space. Clusters will be examined for potential novel subsets of samples - with clinical data used to identify the cause of the clustering with linear and discrete data methods. 2) We will treat counts of each taxa as response, inflammatory cytokine levels as covariates and use negative binomial models (or zero-inflated versions). 3) We will treat cytokine levels as response, relative abundance of each taxa as covariates and use linear models. In these regressions, a pre-treatment indicator and an interaction term between pre-treatment and the covariates will be included. Similar methods will be used to analyze VMI and vaginal pH. **Sample Size and Power**

Rationale: Cytokine levels are continuous variables and even given this small sample size, should allow for more than adequate power to detect large differences in mean concentrations between pre- and post-treatment groups.

D.3.3. Specific Aims – 3 and 4: To observe for quantitative and qualitative changes in the distribution of OTUs among the bladder and rectal microbiomes. **Hypothesis:** Alterations in the bladder and rectal

microbiomes will occur before and after transvaginal therapy (similar to the changes seen in the vaginal microbiome). These specific aims are exploratory.

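### Aim 2 leaves separation of the cytokine and combined profiles to a PCoA plot, with no multivariate test and no use of the pairing

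*Combined protocol and SAP*

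**What the plan says.** Section D.3.2 lists three methods for relating bacterial taxa to cytokines. Within the first, the stated purpose is "To determine if cytokine levels and microbiota contribute to the clustering of women pre- and post-treatment", and the means is that "PCoA will be used to determine if these groups separate in space". No distance, scaling, criterion or pairing comes with it. The linear and discrete data methods mentioned next are for finding the cause of clusters, not for deciding whether the visits differ.

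Three other provisions bear on this:

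- Table 2 in D.3.1 gives the microbiome a formal beta-diversity test, "PERMANOVA or Dirichlet-multinomial distribution with Wald-type test". There the distances are only "represented by PCoA to visualize clustering".
- The Aim 2 plan opens with a marker-by-marker comparison: mean concentrations "will be compared by Student t-test or robust non-parametric tests between pre- and post-treatment samples". Pairing is not stated.
- D.2 sets out a paired design: "The intention of this study is for each of the subjects to serve as her own control", with sampling "at two separate time points".

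D.3.3.1 applies the Aim 2 plan to the bladder and rectal biomarkers, so the same step recurs there, as exploratory work.

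**The concern.** Table 2 keeps display and test apart; the Aim 2 sentence does not. It asks a yes-or-no question about the cytokine and combined profiles and answers it with an ordination. A chance pattern read as separation then carries no error control. A real shift can also be missed, because the plot sets the shift against the total spread of the samples, including stable differences between women, which a paired comparison removes.

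Aim 2 hypothesises an overall fall in inflammatory markers, which is a statement about eight cytokines together. At stake is the one step that looks at them together. The sentence also promises to say whether cytokines and microbiota contribute to the clustering, which a plot cannot show.

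**Working it through.** **The plan's own figure.** This step has none. The only power figure is for Aim 1: a 0.2 rise, SD 0.3, 20 women. As a paired t-test, 0.2/(0.3/√20) = 0.2/0.0671 = 2.98, and with 19 df and two-sided α = 0.05 the power is 80.7%. It reproduces if 0.3 is the SD of within-woman change. It does not bear on PCoA.

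**Inputs from the documents.** 20 treated women, two visits, α = 0.05, and eight cytokines ("IL-1B, IL-4, IL-6, IL-8, IL-10, TNF- α , MCP-1, GM-CSF will be collected at the same time points").

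**Assumed, because the documents give no cytokine variances.** Markers standardised to SD 1; V1-V2 correlation ρ of 0.5 to 0.8; correlation 0.5 among markers across women; visit-noise correlation r_e of 0 or 0.5; all eight markers falling by δ SD. PCoA is on Euclidean distance.

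**Step 1: the plot, by hand.** With a common marker correlation r, axis 1 is close to the average of the eight markers. The distance between visit centres on it, in SD units, is Δ = δ√8/√(1+7r), and the share of samples nearer their own visit's centre is about Φ(Δ/2). With r = 0.5, √(1+7r) = √4.5 = 2.121:

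- δ = 0.3: Δ = 0.849/2.121 = 0.40, Φ(0.20) = 58%
- δ = 0.5: Δ = 1.414/2.121 = 0.67, Φ(0.33) = 63%
- δ = 1.5: Δ = 4.243/2.121 = 2.00, Φ(1.00) = 84%

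ρ does not appear in Δ: for a given marker correlation, the plot gains nothing from the pairing.

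**Step 2: the paired comparison, by hand.** For the average of the eight within-woman changes, the noncentrality is δ√8·√20/√(2(1−ρ)(1+7r_e)), where √8·√20 = 12.65. With r_e = 0.5:

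- ρ = 0.5: denominator √4.5 = 2.121, giving 3.795/2.121 = 1.79 (δ = 0.3) and 6.325/2.121 = 2.98 (δ = 0.5)
- ρ = 0.8: denominator √1.8 = 1.342, giving 2.83 and 4.71

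Against a critical value of 2.09, power is below one half in the weakest case and near one in the strongest.

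**Step 3: simulation of both** (at least 400 trials per setting; permutation test of the distance between visit centres):

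| Shift in all 8 markers | Agreement on axes 1-2 | Within-woman test rejects, independent noise | Within-woman test rejects, noise correlated 0.5 |
|---|---|---|---|
| None | 53-55% | about 3-6% | about 3-6% |
| 0.3-0.5 SD | 58-67% | 73-100% | 37-99% |
| 1.5 SD | about 85-91% | 100% | 100% |

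The no-shift figure exceeds 50% because the centres are estimated from the same samples. The 37% is for 0.3 SD with ρ = 0.5.

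**Step 4: how labels are permuted.** With independent noise and a 0.3 SD shift, permuting visit freely across all samples has power of only 0.02 to 0.11. Its type I error is 0.00 to 0.02, so it is conservative for paired samples.

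**Step 5: other assumptions** (marker correlation 0.3 to 0.6). With 90% of variance between women and a 0.3 SD shift, visit explains 4-6% of axis 1 and at most 1% of axis 2, while the within-woman test has power 0.93-0.99. With a 30% between-woman share, that power is 0.25-0.37, against 0.14-0.24 with free permutation.

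**The case against.** The strongest reply is that this is exploratory ordination in a pilot study. It sits inside one of three methods for relating taxa to cytokines and leads to a search for novel subsets of samples. No primary conclusion or power statement depends on it. That stands, and it limits the severity.

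A reader might infer that the plan judges all pre-post separation by eye. It does not: Table 2 tests the microbiome. Nor could an overlapping plot overturn a cytokine fall, since each marker has its own comparison. If those comparisons are run as paired tests with Benjamini-Hochberg adjustment and noise is correlated 0.5, they find at least one marker in 0.28 to 0.98 of trials, against 0.37 to 0.99 for the profile test. The gain in detection is modest. What remains is that no marker-level test says whether the profile as a whole separates.

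It is also tempting to say that a real shift will look like complete overlap because the axes follow differences between women. PCoA axes follow the largest variation from any source, and the documents do not show that between-woman variation is largest. They claim adequate power only for large differences, and large common shifts do show on the plot. Nor do the documents say that cytokines would enter in raw units; scaling is simply unstated.

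**Conclusion.** The concern holds in a narrow form. For the cytokine profile and the combined profile, Aim 2 asks whether the visits separate and supplies no test, no distance and no use of the pairing. The harm is conditional on assumed variances: for shifts of 0.3-0.5 SD the plot is barely distinguishable from no effect, while a within-woman test has moderate to high power. How high depends mainly on the V1-V2 correlation and on whether visit noise is shared across markers, so such shifts cannot be called easily detectable in general. The missing error control, by contrast, follows from the text and needs no assumption. Severity is minor: a secondary aim of a pilot study, with formal tests alongside.

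**What to change.** Replace the PCoA sentence with text along these lines: *Separation of the V1 and V2 cytokine profiles in treated women will be tested by PERMANOVA on Euclidean distance of log-transformed, standardised cytokines, permuting visit only within woman. PCoA will be shown as a figure with each woman's two visits joined.*

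Also:

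- For the combined profile, state how the two data types are joined and which distance is used, and test it the same way; otherwise call it display only.
- Apply the within-woman restriction to the Table 2 PERMANOVA.
- State that the five untreated women are left out of this test.
- If the contribution of cytokines is to be examined by distance-based regression of the community change, label it exploratory or leave it out: up to eight predictors in 20 women is thin.

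The cost is a few lines of text and code. PERMANOVA is already in the plan, and no new samples or assays are needed.

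### Vaginal pH is cut off below 5 at entry but not at V2, so the planned pre/post comparison of pH–taxon associations is biased towards weak before and stronger after, by an amount the documents do not fix

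*Combined protocol and SAP*

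**What the plan says.** - **Eligibility (D.1, Screening/Eligibility).** One inclusion criterion is "a screening vaginal pH of ≥ 5". No such bound applies at Visit 2.
- **Measurement (D.3.2, Approach).** pH is collected at V1 and V2. The Aim 2 hypothesis expects "concomitant lowering of the vaginal pH", so values below 5 are anticipated at V2.
- **Method 1 (D.3.2, Biostatistical Analysis Plan).** Pearson correlations, with a "heat map showing correlations that are significantly different between pre- and post-treatment groups".
- **Method 3 (same place).** "We will treat cytokine levels as response, relative abundance of each taxa as covariates and use linear models". For the regressions of methods 2 and 3, "a pre-treatment indicator and an interaction term between pre-treatment and the covariates will be included".
- **Extension to pH (same place).** "Similar methods will be used to analyze VMI and vaginal pH".

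The plan does not mention the lower bound on baseline pH, a truncated-response model, or any caution in reading the pH interaction. It does not say whether the screening reading is also the V1 value, or how many women the pH rule turns away.

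**The concern.** Selecting people on the response variable flattens the regression of that response on anything correlated with it, and shrinks the correlation. The entry rule does this to pH at V1. At V2 the selection survives only as far as a woman's V2 values follow her V1 values. Method 3 with pH as response, and the method 1 comparison of correlations, therefore set a flattened V1 association against a less flattened V2 one. The difference is non-zero in expectation with no real change.

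The direction is always the same: the pH–Lactobacillus link looks weak before oestrogen and stronger after it. That is an attractive finding to report from a pilot meant to inform later studies, and eligibility alone can push the estimate that way. Adjusting p-values for multiplicity does not remove a bias.

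**Working it through.** **Plan's own figures.** The plan gives no figure for the pH analysis. Its one power statement (D.3.1: Lactobacillus 0.4 to 0.6, SD 0.3, 20 women, 80%) reproduces as a two-sided paired t-test at 80.7% if 0.3 is the SD of the difference. This point does not affect it.

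**Inputs from the documents.** pH bound 5 at screening; 20 treated women; the same women at both visits (D.2); Lactobacillus share 0.4 ± 0.3 (D.3.1).

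**Assumed, because the documents are silent.** The pH–taxon correlation ρ or slope; the proportion q screened out by the pH rule; the V1–V2 persistence r within a woman; whether screening and V1 are the same reading.

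**Step 1: closed form (bivariate normal, no true change).** Let z = Φ⁻¹(q), λ = φ(z)/(1 − q), and k = 1 + zλ − λ², the fraction of pH variance left after truncation.

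- V1 slope / true slope = k / (1 − ρ²(1 − k))
- V2 slope / true slope = (1 − r²(1 − k)) / (1 − r²ρ²(1 − k))

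Example with ρ = -0.6, q = 0.30, r = 0.5:

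- z = -0.524, λ = 0.348/0.70 = 0.497, k = 1 − 0.260 − 0.247 = 0.493.
- V1: 0.493/(1 − 0.36 × 0.507) = 0.493/0.817 = 0.60, so -0.60 becomes -0.36.
- V2: (1 − 0.25 × 0.507)/(1 − 0.25 × 0.36 × 0.507) = 0.873/0.954 = 0.915, so -0.60 becomes -0.55.
- V1/V2 ratio = 0.60/0.915 = 0.66.

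With q = 0.05, k = 0.81. V1 gives 0.810/0.932 = 0.87, V2 gives 0.969, and the ratio is 0.90. At r = 1 the two expressions are equal for any q and the artefact vanishes.

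**Step 2: the test at n = 20, same example (20,000 simulated trials).** Correlations average -0.46 at V1 and -0.56 at V2. The method 3 interaction is significant in 9.2% of trials, against 2.5% with no screening. That reference rate is below 5% because the model ignores pairing. With the taxon as response and pH as covariate, both slopes are -0.60 and the rate is 3.5%.

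**Step 3: pH scale.** Simulated pH = intercept + slope × share + error, share 0.4 ± 0.3 before screening (held within 0 to 1), 20 women followed to V2, the same relationship at both visits, screening reading equal to the V1 reading. Entries are for r = 0 / 0.5 / 0.8 and are approximate.

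| Slope, residual SD, intercept | Screened out | V1/V2 slope ratio | Interaction significant |
|---|---|---|---|
| -1.5, 0.6, 6.2 | 21% | 0.65 / 0.69 / 0.82 | 11% / 7% / under 1% |
| -2.0, 0.5, 6.2 | 30% | 0.65 / 0.68 / 0.79 | 20% / 12% / 2% |
| -2.0, 0.6, 6.2 | 32% | 0.59 / 0.63 / 0.76 | 19% / 12% / 2% |
| -2.0, 0.5, 6.8 | 10% | 0.83 / 0.87 / 0.93 | 7% / 4% / under 1% |
| -2.0, 0.5, 7.1 | 4% | 0.90 / 0.93 / 0.96 | 5% / 3% / under 1% |

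If screening is a separate reading differing from V1 with SD 0.3, the first three rows fall to about 10–15% / 5–9% / 1%, with ratios about 0.65–0.85. With pH as covariate the V1 and V2 slopes agree within about 13% throughout, and the interaction rate stays at or below 5%.

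**The case against.** The strongest case against is about size and framing, and most of it stands.

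- **The same women are followed.** V2 inherits part of the selection. A false-positive rate near 20% needs V2 values unrelated to V1 values; at persistence 0.8 the rate is under 3%. A reader might infer that the interaction will routinely come out significant. The documents do not support that: even in the worst case shown, about four trials in five show no significant interaction.
- **The screened-out share is unknown.** Eligible women are already at least 55, postmenopausal and clinically diagnosed with vulvovaginal atrophy, so the pH rule may exclude few. With 4–10% excluded, the effect on the test is slight and the slope ratio is 0.83 or higher.
- **The share of 0.4 ± 0.3 describes the enrolled cohort.** The simulation applies it before screening. In the -2.0, 0.5, 6.2 case the enrolled women then have about 0.30 ± 0.22, so these rows are illustrations.
- **The affected term is secondary.** Aim 2 hypothesises that pH falls and that changes correlate with rising Lactobacillus, not that the slope differs by visit. The sentence extending the methods does not itself make pH the response, so the point is conditional on that reading.

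The expected stability in D.2 does not dispose of the point: it concerns untreated women, whereas treatment is meant to change values in the twenty treated, and persistence there is unknown. Nothing in the objection reverses the direction of the bias.

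**Conclusion.** The concern holds as a bias of known direction and unknown size. If the D.3.2 methods are applied to pH with pH as response, or through compared correlations, the V1 association is attenuated relative to V2 by the entry rule. Across the assumed ranges the V1 slope is about 0.6–0.95 of the V2 slope. The false interaction rate at n = 20 runs from below 5% to about 20%, the upper end requiring zero persistence and 20–30% screened out. An indirect bound, from a separate screening reading, weakens the effect but does not remove it.

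It would go too far to say that the interaction measures eligibility and not oestrogen: a real change in slope could be present as well, and the plan gives no means of separating the two. Nor does the point say anything about the mean pre/post change in pH, or about the correlation of changes with changes. Method 2, with pH as covariate, is not biased in this way.

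**What to change.** In the D.3.2 Biostatistical Analysis Plan:

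1. Where V1 and V2 pH–taxon associations are compared, base the comparison on the method 2 direction already planned (taxon as response, pH as covariate).
2. Do not test, or interpret as a treatment effect, the pre/post difference in pH–taxon correlations under method 1 or the pre-treatment interaction under method 3 with pH as response.
3. State that V1 pH is truncated by the entry criterion, say whether the screening reading is the V1 value, and report how many women the pH rule excluded.

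The cost is wording only, with no new data, patients or visits. The pH part of two overlapping secondary comparisons is given up; the mean change in pH and the change-on-change correlations stay. One reservation: the near-absence of bias in the method 2 direction was checked with a linear stand-in, not with the planned negative binomial or zero-inflated model, so it should be described as largely unbiased.
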